To further assess the efficacy of durvalumab treatment in terms of ORR and DoR	ORR according to RECIST 1.1 as assessed by the Investigator DoR according to RECIST 1.1 as assessed by the Investigator
To assess the efficacy of durvalumab treatment in terms of lung cancer mortality	Lung cancer mortality
To further assess the safety and tolerability profile of durvalumab treatment, including all AEs	AEs, SAEs, AESIs, imAEs, physical examinations, vital signs including BP, pulse, ECGs, and laboratory findings including clinical chemistry, hematology, and urinalysis
Exploratory objectives	
CCI	CCI

Objective	Endpoint/variable
CC1 [REDACTED]	CC1 [REDACTED]

AE = Adverse event; AESI = Adverse event of special interest; BP = blood pressure; DoR = Duration of response; CTCAE = Common Terminology Criteria for Adverse Event; CCI
ECG = Electrocardiogram; CCI
CC1 [REDACTED] d
CC1 [REDACTED];
imAE = Immune-mediated adverse events; IP = Investigational product; NCI = National Cancer Institute; ORR = Objective response rate; OS = Overall survival; OS12 = Proportion of patients alive at 12 months from first date of treatment; CCI PFS = Progression-free survival; PFS6, PFS12 = Progression-free survival at 6, 12 months, respectively; CCI
CC1 [REDACTED]; PRAE = Possibly related adverse event; CCI [REDACTED];
RECIST 1.1 = Response Evaluation Criteria in Solid Tumors version 1.1; SAE = Serious adverse event; TL = Target lesion; CCI .

Note: Toxicities will be classified as per CTCAE grading system NCI CTCAE version 5.0. Analysis of ORR and DoR will be based upon Investigator assessment according to RECIST 1.1. Prior irradiated lesions may be considered measurable and selected as TLs providing they fulfill the other criteria for measurability.
Note: An AESI is an AE of scientific and medical interest specific to understanding of the IP. AESIs for durvalumab include, but are not limited to, events with a potential inflammatory or immune-mediated mechanism and which may require more frequent monitoring and/or interventions such as steroids, immunosuppressants, and/or hormone replacement therapy.

Overall design

This is a Phase II open-label, single-arm, multicenter, international study to evaluate the clinical activity of durvalumab in patients with Stage III unresectable NSCLC who are deemed to be ineligible for chemotherapy per Investigator assessment.

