2.3.2.1 Durvalumab

Risks with durvalumab include, but are not limited to, diarrhea/colitis, pneumonitis/ILD, endocrinopathies (ie, events of hypophysitis/hypopituitarism, adrenal insufficiency, hyper- and hypothyroidism, type I diabetes mellitus, and diabetes insipidus), hepatitis/increases in transaminases, nephritis/increases in creatinine, pancreatitis/increases in amylase and lipase, rash/dermatitis, myocarditis, myositis/polymyositis, infusion-related reactions, hypersensitivity reactions, pancreatitis, serious infections, and other rare or less frequent inflammatory events including neuromuscular toxicities (eg, Guillain-Barre syndrome, myasthenia gravis).

For information on all identified and potential risks with durvalumab, please always refer to the current version of the durvalumab IB.

In monotherapy clinical studies, AEs at an incidence of > 20% include events such as fatigue, cough, decreased appetite, dyspnea, and nausea. Approximately 10% of patients discontinued the drug due to an AE. In the PACIFIC Study in patients with Stage III NSCLC following cCRT, AEs (all causality) experienced during the study with an incidence of > 10% (durvalumab vs

placebo) were cough (35.4% vs 25.2%); fatigue (23.8% vs 20.5%); dyspnea (22.3% vs 23.9%); radiation pneumonitis (20.2% vs 15.4%); diarrhea (18.3% vs 18.8%); pyrexia (14.7% vs 9%); decreased appetite (14.3% vs 12.8%); nausea (13.9% vs 13.2%); pneumonia (13.1% vs 7.7%); pneumonitis (12.6% vs 7.7%); arthralgia (12.4% vs 11.1%); pruritus, rash and upper respiratory tract infection (12.2% each vs 4.7%, 7.3% and 9.8%, respectively); constipation (11.8% vs 8.5%); hypothyroidism (11.6% vs 1.7%); headache (10.9% vs 9.0%); asthenia (10.7% vs 13.2%); and back pain (10.5% vs 11.5%). Combined events of pneumonitis or radiation pneumonitis occurred in 33.9% vs 24.8% of patients, including CTCAE Grade 3 pneumonitis or radiation pneumonitis in 3.4% vs 2.6% of patients; no patients in either treatment group reported Grade 4 events of pneumonitis or radiation pneumonitis.

Please see the current version of the IB for a detailed summary of the monotherapy data including AEs, serious adverse events (SAEs), and CTCAE Grade 3 to 5 events reported across the durvalumab program.

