8.2.3 Vital signs

Vital signs (blood pressure [BP], pulse, temperature, and respiration rate) will be evaluated according to the SoAs. Body weight is also recorded at each visit along with vital signs.

First infusion

On the first infusion day, patients will be monitored and vital signs collected/recorded in eCRF prior to, during, and after infusion of IP as presented in the bulleted list below.

BP, pulse, temperature, and respiration rate will be collected from patients before, during, and after the first infusion at the following times (based on a 60-minute infusion):

- Prior to the beginning of the infusion (measured once from approximately 30 minutes before up to 0 minutes [ie, the beginning of the infusion])
- Approximately 30 minutes during the infusion (**halfway** through infusion)
- At the end of the infusion (approximately 60 minutes \pm 5 minutes)

If the infusion takes longer than 60 minutes, then BP, pulse, temperature, and respiration rate measurements should follow the principles as described above or be taken more frequently if clinically indicated. A 1-hour observation period is recommended after the first infusion of durvalumab.

Subsequent infusions

BP, pulse, and other vital signs should be measured, collected/recorded in eCRF prior to the start of the infusion. Patients should be carefully monitored and BP and other vital signs should be measured during and postinfusion as per institution standard and as clinically indicated. Any clinically significant changes in vital signs should be entered onto an unscheduled vital signs CRF page.

Situations in which vital signs results should be reported as AEs are described in Section 8.3.7. For any AEs of infusion reactions, the vital signs values should be entered into the CRF.

8.2.4 **Electrocardiograms**

Resting 12-lead ECGs will be recorded at screening and as clinically indicated throughout the study (see the SoAs). ECGs should be obtained after the patient has been in a supine position for 5 minutes and recorded while the patient remains in that position.

In case of clinically significant ECG abnormalities, including a QTcF (QT interval corrected for heart rate using Fridericia's formula) value > 470 ms, 2 additional 12-lead ECGs should be obtained over a brief period (eg, 30 minutes) to confirm the finding.

Situations in which ECG results should be reported as AEs are described in Section 8.3.7.

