#### 1.1.2 Secondary Objectives

Secondary Efficacy Objectives	Endpoints / Variables
To assess the efficacy of durvalumab treatment in terms of progression-free survival (PFS) and overall survival (OS)	Median PFS according to Response Evaluation Criteria in Solid Tumors version 1.1 (RECIST 1.1) as assessed by the Investigator PFS6 and PFS12 according to RECIST 1.1 as assessed by the Investigator Median OS and OS12
To further assess the efficacy of durvalumab treatment in terms of objective response rate (ORR) and duration of response (DoR)	Objective response (OR) according to RECIST 1.1 as assessed by the Investigator DoR according to RECIST 1.1 as assessed by the Investigator
To assess the efficacy of durvalumab treatment in terms of lung cancer mortality	Lung cancer mortality

Secondary Safety Objectives	Endpoints / Variables
To further assess the safety and tolerability profile of durvalumab treatment, including all adverse events (AEs)	AEs, serious adverse events (SAEs), adverse events of special interest (AESIs), immune-mediated adverse events (imAEs), physical examinations, vital signs including blood pressure (BP) and pulse rate, electrocardiograms (ECGs) and laboratory findings including clinical chemistry, haematology and urinalysis

Note: Analysis of OR and DoR will be based upon Investigator assessment according to RECIST 1.1. Prior irradiated lesions may be considered measurable and selected as target lesions provided they fulfil the other criteria for measurability.

[figure not shown]
An AESI is an AE of scientific and medical interest specific to the understanding of durvalumab. AESIs for durvalumab include, but are not limited to, events with a potential inflammatory or immune-mediated mechanism and which may require more frequent monitoring and/or interventions such as steroids, immunosuppressants and/or hormone replacement therapy.

An imAE is defined as an AESI that is associated with drug exposure and is consistent with an immune-mediated mechanism of action and where there is no clear alternate etiology.

[figure not shown]

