### 3.2.4      **Electrocardiograms**

These measurements are recorded as detailed in the study schedule (See [Appendix A](#)). If vital signs, ECG and blood draws for laboratory tests are scheduled at a visit, they will always be performed in the order: ECG, vital signs and then blood draws.

At Screening, and as clinically indicated throughout the study, ECGs should be obtained after the patient has been in a supine position for 5 minutes and recorded while the patient remains in that position. From these resting 12-lead ECGs values of the QT and RR intervals and the QT interval corrected for heart rate using Fridericia's correction (QTcF) is derived using the following formula:

- $QTcF = QT/RR^{(1/3)}$  where RR is in seconds

In case of clinically significant ECG abnormalities, 2 additional 12-lead ECGs will be performed. All three ECGs should include a value of QTcF over a brief period (eg, 30 minutes). A QTcF value  $>470$  msec will confirm the ECG abnormality finding.

The value of QTcF will be re-derived from the values of RR and QT during the creation of the reporting database.

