#### **4.1.2 General Considerations for Summary of Safety Data**

The following considerations are for the summary of safety data.

- The missing values in ECG, vital signs, laboratory data, coagulation and urinalysis will not be imputed.
- If triple ECGs are performed, the mean value of any continuous parameters of the ECG will be derived first and it will be used as the value of the ECG at that timepoint/assessment. For abnormalities, the worst case will be used for any summary tables.
- If a laboratory value is reported as <LLQ (where ‘LLQ’ is the lower limit of quantification), then LLQ value will be used to impute ‘<LLQ’ for the summary tables. In the data listings, this value will be listed as reported <LLQ.
- Any TEAEs with missing causality data will be considered as related to the durvalumab.
- Any partial dates will be presented as reported in the data listings. The partial dates will be imputed for the derivation of time to resolution, time to onset etc. using the criteria given in Section 4.1.3.

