#### **4.5.2 Electrocardiograms**

The data for the ECG are used for safety monitoring and to identify AEs. No summaries or listings will be created.

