## **6. CHANGES OF ANALYSIS FROM PROTOCOL**

No summary output or listings will be produced for ECG parameters as ECG data is only used for safety monitoring and to identify AEs. For vital sign parameters only box plots will be produced.

CCI

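### ECG is a declared secondary safety endpoint, but the SAP gives it no summary or listing, and this contradicts SAP rules still in force

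*SAP*

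**What the plan says.** **Endpoint.** The protocol synopsis includes ECG among the variables for the secondary safety objective: "vital signs including BP, pulse, ECGs, and laboratory findings including clinical chemistry, hematology, and urinalysis". SAP 1.1.2 does the same ("electrocardiograms (ECGs) and laboratory findings including clinical chemistry, haematology and urinalysis"), and SAP 3.2.2 gives ECG its own entry.

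**Planned analysis in the protocol.** Section 9.5.2.1 defines the baseline value for change-from-baseline summaries of several data types, ECG among them. It also gives the formula by which QTcF is derived in the reporting database.

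**Schedule.** Table 1 and section 8.2.4 of the protocol require an ECG at screening and afterwards only when clinically indicated. Table 2 (follow-up) has no ECG row.

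**Output in the SAP.** SAP 4.5.2 says: "The data for the ECG are used for safety monitoring and to identify AEs. No summaries or listings will be created". SAP 6 says: "No summary output or listings will be produced for ECG parameters as ECG data is only used for safety monitoring and to identify AEs".

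**ECG rules the SAP keeps.** SAP 3.2.4 says: "The value of QTcF will be re-derived from the values of RR and QT during the creation of the reporting database". SAP 4.1.2 averages triplicate readings and adds: "For abnormalities, the worst case will be used for any summary tables". SAP 4.1.1 and 4.1.4 also still provide for ECG data, as set out under the working.

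**Route from ECG to AE.** Protocol 8.2.4 says: "Situations in which ECG results should be reported as AEs are described in Section 8.3.7".

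**The concern.** An endpoint that both documents declare should lead to something a reader of the study report can see. Here it does not, and the justification is that the AE data carry the information instead. That works only as far as ECG findings are entered as AEs, and the protocol section meant to say when this happens does not mention ECG.

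Two things are at stake. First, the SAP cannot be programmed as written, because one section orders ECG data to be summarised and listed and another forbids both. Second, no planned output would show how many patients had an ECG after starting durvalumab, or how many of them had a QTcF above the 470 ms value that both documents use. This bears on a trial whose main goal is safety and whose protocol names myocarditis among the drug's risks (section 2.3.2.1: "rash/dermatitis, myocarditis, myositis/polymyositis, infusion-related reactions, hypersensitivity").

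**Working it through.** No formula applies, because the point rests on no rate, power or sample size. The check sets the provisions side by side.

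**Step 1: the SAP against itself.** SAP 4.5.2 and 6 allow no ECG summary and no ECG listing. The other ECG text in the current SAP is:

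| SAP section | What it provides for ECG | Relation to 4.5.2 |
|---|---|---|
| 4.1.1 | ECG data from unscheduled visits go into the summaries | Direct contradiction (summaries) |
| 4.1.1 | All collected data, scheduled or not, go into the patient listings | Direct contradiction (listings) |
| 4.1.2 | Mean of triplicates for continuous values; worst case for abnormalities in summary tables | Presumes tables that do not exist |
| 4.1.4 | Time windows defined for ECG summaries | Presumes summaries that do not exist |
| 3.2.4 | QTcF re-derived; a value above 470 msec confirms an abnormality | A derivation and a criterion that no output uses |

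The two provisions in 4.1.1 cannot be followed together with 4.5.2. The other three are leftovers rather than flat contradictions, since they only say how ECG data would be handled if shown. The amendment history dates the removal of ECG output to 7 May 2021. The sections in the table still carry ECG rules.

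**Step 2: the stated reason against the protocol.** SAP 4.5.2 and 6 rely on ECGs being used to identify AEs. Protocol 8.2.4 sends the site to 8.3.7 for the rule. Section 8.3.7 gives specific rules for laboratory tests, vital signs and physical examination, and none for ECG. It does have a generic clause: without signs or symptoms, clinically relevant worsening in a parameter that the protocol does not mandate is reported as an AE. On-treatment ECGs are done only when clinically indicated, so they can be read as falling under that clause. The AE definition in Appendix B 1, which covers any unfavourable and unintended sign, points the same way. The route is therefore generic and partly a matter of inference, but it exists.

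**Step 3: what reaches the report and what does not.**

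- An ECG finding entered as an AE reaches the AE tables and listings (SAP 4.5.1).
- Myocarditis reported as an event is a predefined category in SAP 3.2.3.2. SAP 4.5.1.1 summarises these categories by grade, seriousness, outcome, treatment, discontinuation and time to onset.
- An ECG abnormality not entered as an AE, including a QTcF above 470 ms, appears nowhere.
- The number of patients with any on-treatment ECG appears nowhere.

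**Result.** There is one declared endpoint and there are zero outputs. The documents do not say how many on-treatment ECGs are expected, so the number of affected patients cannot be derived. About 102 patients are treated and each has a screening ECG, but an unreported screening ECG says nothing about safety on treatment.

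**The case against.** The removal was deliberate and disclosed. SAP 6 exists to record departures from the protocol, gives the reason, and is matched by an entry in the amendment history. A specific section can also be taken to override a general one, and SAP 4.1.1 allows specific deviations. With no scheduled ECG after screening, by-visit summaries would describe a small and clinically selected group. ECG is one item in a long list serving a single objective, and the AE tables answer most of that objective.

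Much of this stands. By-visit means would be uninformative, and the sponsor may drop them. Disclosure does not cure the rest: ECG remains in both endpoint lists, and 4.1.1 still orders what 4.5.2 forbids. SAP 4.1.1 also expects a deviation to be noted on the relevant output, and here there is no output on which to note it.

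A reader might be tempted to infer three stronger things, none of which the documents support:

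- **That the protocol gives ECG findings no way of becoming AEs.** The generic clause in 8.3.7 and the AE definition provide one. Only an ECG-specific rule is missing.
- **That cardiac immune toxicity will be under-reported.** Nothing in the documents links QTcF to myocarditis or suggests that cardiac events will be missed, and reported myocarditis is counted in its own right.
- **That some particular share of patients is affected.** No figure in either document anchors such a share.

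**Conclusion.** The point holds in a limited form. A declared secondary safety endpoint has no output. The section that removes it contradicts SAP 4.1.1 and leaves the rules in 3.2.4, 4.1.2 and 4.1.4 idle. The AE route offered in its place rests on a protocol cross-reference to a section with no ECG-specific rule. What is lost is confined to ECG abnormalities not entered as AEs and to the count of patients who had an on-treatment ECG.

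This is a cheap improvement, not a threat to the trial's conclusions. The primary endpoint, Grade 3 and Grade 4 possibly related AEs within six months, is analysed from AE records and does not depend on ECG output. The conclusion assumes that QT and RR are recorded for clinically indicated ECGs, as SAP 3.2.4 implies. It also assumes that 4.1.1 was not meant to be silently overridden by 4.5.2.

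**What to change.** Replace SAP 4.5.2 and the ECG sentence in SAP 6 with two outputs:

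1. A listing of all post-baseline ECGs, showing the screening value, the re-derived QTcF and any recorded clinically significant abnormality.
2. A count, overall and for the standard and palliative radiotherapy cohorts, of patients with any post-baseline ECG and, among them, of those with QTcF above the 470 ms already in the documents or a recorded clinically significant abnormality. Label it as clinically indicated ECGs only, and produce no by-visit means.

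Keep the QTcF derivation in 3.2.4 and the triplicate rules in 4.1.2. State whether the 470 ms count uses the triplicate mean or the worst reading, since 4.1.2 provides for both. Align 4.1.1, 4.1.2 and 4.1.4 with these two outputs.

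In the protocol, 8.2.4 and 8.3.7 must be reconciled so that the cross-reference leads to text that covers ECG. What the reporting rule should be is for the sponsor to decide.

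The cost is one listing and one short table, from QT and RR data that the SAP already processes. Whether an overall ECG interpretation is captured in the database is not established, so the abnormality item depends on what is recorded. The downside is that post-baseline ECGs come from a clinically selected subset, so the count cannot be read as an incidence in all treated patients and must carry that caveat. If the sponsor still wants no ECG output, the consistent alternative is to take ECG out of the endpoint lists and delete the unused rules.

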#### 4.5.3 Vital Signs

Box plots of the vital signs results by visit will be presented.

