8.3.7 Adverse events based on examinations and tests

The results from the Clinical Study Protocol-mandated laboratory tests and vital signs will be summarized in the clinical study report (CSR). Deterioration as compared to baseline in protocol-mandated laboratory tests and vital signs should therefore only be reported as AEs if they fulfill any of the SAE criteria or are the reason for discontinuation of treatment with the IP.

If deterioration in a laboratory value/vital sign is associated with clinical signs and symptoms, the sign or symptom will be reported as an AE and the associated laboratory result/vital sign will be considered as additional information. Wherever possible, the reporting Investigator uses the clinical rather than the laboratory term (eg, anemia versus low hemoglobin value). In the absence of clinical signs or symptoms, clinically relevant deteriorations in nonmandated parameters should be reported as AE(s).

Deterioration of a laboratory value that is unequivocally due to disease progression should not be reported as an AE/SAE.

Any new or aggravated clinically relevant abnormal medical finding at a physical examination as compared with the baseline assessment will be reported as an AE unless unequivocally related to the disease under study (see Section [8.3.9](#)).

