### 3.2.5      **Vital Signs**

Vital signs measurements will be collected at the start of each treatment cycle as detailed in the schedule of assessment ([Appendix A](#)).

Measurements will include respiration rate (breaths/minute), SBP (mmHg), DBP (mmHg), pulse rate (beats/min), weight (kg), height (cm) and body temperature (degrees Celsius).

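### Vital signs get by-visit box plots only, which do not show within-patient change and leave out two of the three first-infusion readings

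*SAP*

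**What the plan says.** **AE rule.** Protocol 8.3.7 states that the mandated "laboratory tests and vital signs will be summarized in the clinical study report (CSR"). It then draws a consequence: deterioration from baseline "should therefore only be reported as AEs if they fulfill any of the SAE criteria or are the reason for discontinuation" of treatment. One further route stays open: "If deterioration in a laboratory value/vital sign is associated with clinical signs and symptoms, the sign or symptom will be reported as an AE".

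**Collection.** Under protocol 8.2.3, on the first infusion day "patients will be monitored and vital signs collected/recorded in eCRF prior to, during, and after infusion of IP". The timepoints are before the start, about 30 minutes in, and at the end. The same section adds: "For any AEs of infusion reactions, the vital signs values should be entered into the CRF".

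**Planned analysis.** Protocol 9.5.2.1 defines the baseline value to be used in change-from-baseline summaries, and vital signs are among the data types it names. SAP 3.2.5 describes collection more narrowly: "Vital signs measurements will be collected at the start of each treatment cycle as detailed in the schedule of assessment". It does not mention the mid- and end-infusion readings. The only planned output is in SAP 4.5.3: "Box plots of the vital signs results by visit will be presented". SAP 6 declares this as a change from the protocol: "For vital sign parameters only box plots will be produced". Vital signs, including blood pressure and pulse, are a named secondary safety endpoint (SAP 1.1.2 and 3.2.2).

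**The concern.** Protocol 8.3.7 makes a trade. Investigators need not report certain vital-sign changes as AEs, because the CSR will summarise the vital signs themselves. The quantity being traded is deterioration relative to the patient's own baseline. The SAP later cut the summary down, but the AE rule that relied on it was left in place.

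Two things could then go unseen in the report's tables and figures. One is change from baseline within a patient at any visit. The other is what happens to blood pressure, pulse, temperature and respiration during the first infusion, which the protocol takes the trouble to measure three times. At stake is the description of a secondary safety endpoint in a trial whose main purpose is safety.

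**Working it through.** The plan gives no figure to reproduce here. The check sets the sections side by side and then counts readings.

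**1. Where each kind of vital-sign deterioration appears**

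| Kind of change | Where it is captured |
|---|---|
| Meets an SAE criterion | AE data (protocol 8.3.7) |
| Reason for stopping durvalumab | AE data (8.3.7) |
| Accompanied by signs or symptoms | AE data, under the sign or symptom (8.3.7) |
| Part of an infusion or hypersensitivity reaction | AESI, with vital-sign values in the CRF for infusion reactions (8.3.12, 8.2.3) |
| None of these | Vital-sign output in the CSR only |

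Only the last row depends on SAP 4.5.3.

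**2. What the CSR output contains.** Protocol 8.3.7 treats laboratory tests and vital signs alike. For continuous haematology and chemistry parameters, SAP 4.5.4 names both absolute values and change from baseline by visit, and adds shift tables. For vital signs, SAP 4.5.3 names only results. The contrast makes absolute values the natural reading, though the SAP does not use those words. A by-visit box plot of absolute values shows how the group is distributed at each visit. It does not link a patient's value to that patient's baseline. SAP 4.1.4.1 has a rule for maximum and minimum summaries that uses all on-treatment values, but no vital-sign summary calls on it.

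**3. Which Day 1 reading is plotted.** SAP 4.1.4.1 gives vital signs a first window of Day 1 alone. For visit-based summaries it takes one value per patient per window, the one nearest the scheduled date, and the earlier one in a tie. All three first-infusion readings fall on Day 1, so they tie and the pre-infusion reading is kept. That reading is also the last one before the first dose, which is the SAP's definition of baseline (4.1.1). The Day 1 box would then contain no reading taken after dosing began.

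There is one exception. For a CTCAE-gradable parameter with two values on a day, the higher grade is used. The SAP plans CTCAE grading only for AEs and laboratory parameters, so this route is not expected to apply. If it did, a mid- or end-infusion value could enter the box without a label. In either case at most one of three readings is plotted.

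**4. Count of first-infusion readings per parameter.** Inputs are about 102 treated patients, 59 Standard and 43 Palliative (protocol 9.2, SAP 1.3), and 3 timepoints (protocol 8.2.3). Complete collection is assumed, so these are upper bounds.

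- Readings taken: 102 × 3 = 306.
- Plotted at most: 102 × 1 = 102, or 1 in 3.
- In no table or figure: 306 − 102 = 204, made up of 59 × 2 = 118 (Standard) and 43 × 2 = 86 (Palliative).

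**The case against.** The reduction is deliberate and disclosed in SAP 6, and protocol 9.4 leaves the details of analyses to the SAP. Protocol 8.3.7 promises a summary without saying in what form. Box plots are a summary, and under SAP 4.1.1 they would be shown overall and by cohort, so a group shift between Day 1 and later visits would be visible. First-infusion readings serve bedside monitoring first, and SAP 4.1.1 provides for listing all collected data. With no control arm, mean change could not be attributed to durvalumab.

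Much of this stands. There is no hidden contradiction, and the box plots honour part of the 8.3.7 premise. What remains is that SAP 6 gives a reason for dropping ECG output but none for reducing vital signs, and that the AE restriction was not revisited. Listings are not the summary that 8.3.7 relies on, and SAP 6, read literally, leaves even those uncertain for vital signs.

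A reader might go further and infer that most vital-sign deterioration is lost, or that infusion reactions go unreported. The documents do not support either. They give no breakdown of deterioration by type, and the first four rows of the table in the working remain in the AE data. Nor is the lack of a vital-signs output for AESIs in SAP 4.5.1.1 a departure from protocol 9.4 item 6(f), because the lead-in to that list makes its items optional.

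**Conclusion.** The point holds in a limited form. Change in vital signs that is free of symptoms, non-serious and does not stop treatment is kept out of the AE data on the strength of a CSR summary, and the planned summary does not show it as change within a patient. Two of every three first-infusion readings per parameter reach no table or figure.

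This rests on reading *results* as absolute values and on applying the one-value-per-window rule as written. The count of 204 in 306 also assumes complete collection in 102 patients. It measures planned readings, not harm missed, and nothing in the documents shows that a safety conclusion would change. The primary endpoint is unaffected. It is a minor priority, worth doing because it is cheap.

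**What to change.** Amend three places in the SAP:

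- **SAP 3.2.5:** name the three first-infusion timepoints.
- **SAP 4.5.3:** show Cycle 1 Day 1 vital signs by timepoint (pre-, mid- and end-infusion), exempt from the one-value-per-window rule. Add one descriptive table, overall and by cohort, with (a) change from pre-infusion to mid- and end-infusion, and (b) worst on-treatment change from baseline, maximum and minimum, per parameter, using the extreme-value rule already in 4.1.4.1.
- **SAP 6:** revise the box-plots-only statement to match.

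The cost is one extra table and some programming, from data the protocol already requires in the eCRF. No new assessments are needed. The table would be descriptive only, since there is no control arm.
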